## 2 Study Objectives

### 2.1 Primary Objective

The primary objective of the study is to compare the mean length of pre-delivery hospitalization among women undergoing induction of labor with a Foley catheter in the outpatient setting as compared to usual care in the inpatient setting.

### 2.2 Secondary Objective

Our secondary objectives are as follows:

- 1) To compare the cesarean delivery rate among women undergoing outpatient Foley versus inpatient cervical ripening.
- 2) To compare other maternal outcomes including: postpartum hemorrhage, infection, hospital readmission, and satisfaction with the induction process.
- 3) To compare neonatal outcomes including: APGAR scores, umbilical artery pH, and nursery disposition.

## 3 Study Design

### 3.1 General Design

The study began as a randomized control trial. The intervention group was comprised of low risk pregnant women who had a Foley catheter placed followed by dismissal home with return in approximately 12 hours for continuation of the labor induction process. The control group consisted of women who remained inpatient during the entire cervical ripening phase followed by continuation of the labor induction process in the inpatient setting.

Due to difficulty enrolling women for the randomized control trial, a prospective design with an outpatient intervention group (Foley catheter) and matched inpatient control comparison group is proposed. Low risk pregnant women will be invited to participate in an outpatient Foley catheter intervention to begin their induction of labor process. Maternal/Neonatal outcomes and maternal satisfaction with the induction experience will be assessed. The comparison group will be enrolled to participate in the study in a limited way, providing responses to a maternal satisfaction of induction survey and allowing their and their baby's electronic medical record to be followed for maternal/neonatal health outcomes and total hospital time.

- I. Enrollment of participants (Randomized Control Trial)
  - A. Clinic nurses, clinical assistants who room patients, and the patient's obstetric provider will refer eligible patients to the research coordinator.
  - B. The Co-PI ([name]) will monitor the induction scheduling book in the Family Birth Center two weeks in advance to identify patients who may be eligible for the study. She will communicate the patient's next clinic appointment to the research coordinators so these patients can be approached in clinic.
  - C. Patients who receive their care in Mayo Clinic Family Medicine clinics will be eligible for this study. Their providers will be educated regarding this trial.
- II. Patient education, consent, and randomization
  - A. The patients will be educated about induction of labor, the Foley catheter, and the proposed research study.
    1. The patient will be approached for this education during their last or second to last clinic visit before planned induction of labor.
    2. The education will be performed by a trained research coordinator, Principal Investigator, Co-Principal Investigator, or authorized obstetric provider.
  - B. If the patient elects participation, she will undergo informed consent at that time.
    1. Informed consent will be obtained by a trained research coordinator, Principal Investigator, Co-Principal Investigator, or authorized obstetric provider.
  - C. Randomization
    1. Randomization will occur the day before the planned induction to decrease drop out (for example: from spontaneous labor between the clinic visit and planned induction).
    2. The randomization will be computer generated.
    3. The patient's randomization status will be accessed by the research coordinator.
    4. The research coordinator will contact the patient by phone to inform her of her randomization group.

5. Randomization will be stratified by parity (primiparous vs. multiparous) and by body mass index (current body mass index  $<30 \text{ kg/m}^2$  vs.  $\geq 30 \text{ kg/m}^2$ ).

### III. Enrollment of participants (Prospective Study)

#### A. Enrollment of outpatient intervention participants

1. Clinic nurses, clinical assistants who room patients and the patient's obstetric provider will refer eligible patients to the research coordinator.
2. The study coordinator will screen the induction scheduling book in the Family Birth Center weekly to identify patients who may be eligible for the study. She will communicate with eligible women by telephone share general information about the study. If women are interested in learning more, she will meet with them at the patient's next clinic appointment.
3. Patients who receive their care in Mayo Clinic Family Medicine clinics will be eligible for this study. Their providers will be educated regarding this study. These women will be enrolled in the same manner as women from the antenatal clinic.

- (a) Patient education and consent
  - (a) The patients will be educated about induction of labor, the Foley catheter, and the proposed research study.
  - (b) If the patient elects participation, she will undergo informed consent at that time by a trained research study coordinator, Principal Investigator, Co-Principal Investigator, or authorized obstetric provider.
  - (c) Parity (primiparous vs. multiparous) and BMI (current body mass index  $<30 \text{ kg/m}^2$  vs.  $\geq 30 \text{ kg/m}^2$ ) will be recorded based on the stratification used in the Randomized Control Trial design.

#### B. Enrollment of inpatient comparison (usual care) participants

1. Women who decline participation in the outpatient intervention study may be approached to participate in a limited way as inpatient comparison control participants.
2. The study coordinator will screen the OB White Board daily in the Family Birth Center to identify patients presenting for induction of labor who may be eligible for the study, but not captured during the weekly screening process. Eligible women will be approached, after discussion with their attending obstetric provider, to participate in the study as inpatient comparison usual care participants.
3. Four inpatient comparison control participants will be enrolled with the same parity and BMI strata for every outpatient intervention patient enrolled (see III. A. 3. c. above).

- (a) Patient education and consent
  - (a) The patients will be educated the proposed research study.
  - (b) If the patient elects participation, she will undergo informed consent at that time by a trained research study

coordinator, Principal Investigator, Co-Principal Investigator, or authorized obstetric provider.

**IV. Protocol for the intervention group (Both Randomized Control Trial and Prospective Study)**

- A. The patient will present to the Family Birth Center at 0730 or 1930.
- B. A nonstress test (NST) will be performed
  - 1. The fetal heart rate (FHR) is observed by external monitoring for at least 20 minutes. The FHR is observed for the presence of accelerations, at least 2 in 40 minutes that peak at least 15 beats per minute above the baseline and last for at least 15 seconds. The absence of at least 2 accelerations in up to 40 minutes is considered nonreactive.
  - 2. A nonreactive NST, the presence of  $\geq 3$  variable decelerations in a 20 minute period, late-appearing decelerations, or any deceleration lasting  $\geq 1$  minute should be considered criteria for exclusion.
- C. An ultrasound will be performed for fetal presentation and amniotic fluid index.
- D. A cervical exam will be performed with calculation of a Bishop score.
- E. The patient will be asked the following standard questions.
  - 1. Are you experiencing any of the following: regular, painful contractions? Decreased fetal movement? Vaginal bleeding? Leakage of fluid from the vagina concerning for rupture of membranes? Fevers or chills?
  - 2. She will be excluded from the trial based on her answers, as described in section 4.2 "Exclusion Criteria."
- F. A Foley catheter will be placed if the following criteria have been met: the nonstress test is reactive, the fetal presentation is cephalic, the amniotic fluid index is 5 centimeters or more, the Bishop score is  $<9$ , the cervical dilation is  $<3$  cm, and she has no other clinical characteristics that exclude her from the trial.
- G. An obstetric provider will place a 16 French Foley catheter through the internal os. The balloon will be inflated with 60cc of normal saline. The distal end of the Foley will be taped to the patient's inner thigh.
- H. The fetal heart rate tracing will be monitored for 1 hour after Foley placement.
- I. The patient will be sent home if the following criteria are met: the fetal heart rate tracing is reactive and category I; there is no evidence of rupture of membranes, spontaneous labor, or vaginal bleeding more than spotting; and maternal vital signs are within normal range.
- J. Pain control options
  - 1. While the Foley catheter is in place, the patient can use the following non pharmacologic methods to decrease discomfort: warm baths, massage, frequent position changes in a comfortable environment, relaxation techniques, and gentle stretching
  - 2. Pharmacologic methods available to the patient include:
    - (a) Tylenol 1000mg orally q6 hours as needed for pain
    - (b) Morphine 10 mg IM once prior to dismissal
- K. The patient will be instructed to return to the Family Birth Center approximately 12 hours following their Foley bulb placement.
- L. The patient will be given verbal and written instructions as follows:

1. To return immediately to the Family Birth Center if she feels decreased fetal movement, if she is concerned her membranes ruptured, if she has vaginal bleeding more than spotting, if she has regular, painful contractions, if she has severe pain, if she develops a fever of  $\geq 100.4\text{F}$  or  $\geq 38.0\text{ C}$ , or if she develops any symptoms concerning to her.
2. If the Foley catheter is expelled at home, she is to record the time of expulsion. She does not need to return to the Family Birth Center earlier than planned due to expulsion.
3. She will be provided with the 24 hour direct access line for the Family Birth Center to call with any questions or concerns.

M. On arrival to the Family Birth Center at 12 hours later, the induction will be continued.

1. The providing team will decide to proceed with oxytocin and/or artificial rupture of membranes.
2. The oxytocin dose will be increased as determined by the Family Birth Center oxytocin low dose infusion regimen.
3. The patient will have continuous electronic fetal monitoring.
4. The remainder of her care during the first, second, and third stages of labor will be at the discretion of the providing team.
5. If the Foley is still in place when the patient arrives, a provider should gently tug on it. If it does not come out, the providing team may choose to deflate and remove the Foley catheter (and then proceed with artificial rupture of membranes or oxytocin) OR leave the Foley in situ and place vaginal misoprostol.

N. All patients' labor progress will be monitored using a partogram. Cesarean delivery will not be performed for arrest of labor or failed induction unless all criteria have been met as outlined by the Family Birth Center Workgroup protocol made effective 6/2/14.

V. Protocol for the control group (Randomized Control Trial)

A. If the patient is in the outpatient control group, she will arrive to the Family Birth Center at a standard, predetermined time (typically 0730 or 1930) to undergo induction of labor.

B. Method of cervical ripening

1. The only pharmacologic cervical ripening agent to be used is vaginal misoprostol, 25 mcg every 4 hours with a maximum of six doses.
2. She may or may not have a Foley catheter placed as a method of cervical ripening based upon the providing team's discretion.
3. A Foley catheter will be favored during the cervical ripening phase if there is tachysystole and/or a nonreassuring fetal heart tracing precluding further misoprostol administration, provided the Bishop score is still  $<6$ .

C. After cervical ripening is achieved, oxytocin and/or artificial rupture of membranes will be used at the discretion of the providing team.

D. If oxytocin is used during the labor induction, the dose will be increased as determined by the Family Birth Center Oxytocin low dose infusion regimen.

E. The remainder of her care during the first, second, and third stages of labor will be at the discretion of the providing team.

F. All patients' labor progress will be monitored using a partogram. Cesarean delivery will not be performed for arrest of labor or failed induction unless all criteria have been met as outlined by the Family Birth Center Workgroup protocol made effective 6/2/14.

VI. Protocol for the inpatient usual care group (Prospective Study)

A. All methods of cervical ripening and labor augmentation will be at the discretion of the providing team. Cervical ripening will occur as described above with vaginal misoprostol and a Foley catheter; dinoprostone (vaginal prostaglandin, brand name Cervidil) is infrequently used in the Family Birth Center but would now be an option as well. Oxytocin dosing will be increased by the FBC oxytocin low dose infusion regimen, labor will be monitored using a partogram, and Cesarean delivery will continue to be determined by the criteria as described above.

VII. Follow-up

[figure not shown]
A. Inpatient follow-up

1. We will obtain maternal consent to abstract secondary endpoints as described in section 3.3 from the fetal and maternal electronic medical record.

[figure not shown]
B. Follow-up over 6 weeks

1. Secondary endpoints from section 3.3 will be abstracted from the EMR.  
2. Data collection will stop at 42 days after the patient's delivery or the date of the patient's final postpartum clinic visit, whichever comes last.

VIII. Flow chart for Randomized Control Trial

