### 3.3 Secondary Study Endpoints

#### I. Baseline maternal data

##### A. Date of birth

- B. Race and ethnicity
- C. Pre pregnancy body mass index
- D. Gravidity
- E. Parity
- F. Medical comorbidities
- G. Surgical history
- H. Major complications during this pregnancy (i.e. gestational diabetes)
- II. Intervention (outpatient) group data
  - A. Method of Foley catheter insertion: digital or sterile speculum
  - B. Foley catheter expulsion at home: yes/no, time of expulsion
  - C. Return to the Family Birth Center earlier than scheduled and reason (labor, rupture of membranes, decreased fetal movement, vaginal bleeding, pain, fever, or other)
  - D. Bishop score before Foley placement
  - E. Bishop score on the morning of admission for continuation of the labor induction
  - F. First induction method used after admission in the morning
    - a. Oxytocin
    - b. Artificial rupture of membranes
    - c. Oxytocin + artificial rupture of membranes
    - d. If Foley catheter still in place, Foley + oxytocin
- III. Procedural data for both groups
  - A. Gestational age at delivery
  - B. Primary providing team in the Family Birth Center (Obstetrics, Midwifery, or Family Medicine)
  - C. Use of Foley catheter: yes/no, date and time
  - D. Use of pharmacologic cervical ripening: yes/no, date and time, number of doses
  - E. Use of oxytocin: yes/no, date and time, maximum dosage
  - F. Rupture of membranes: spontaneous or artificial, date and time
  - G. Epidural placement: yes/no, date and time
  - H. IV pain medication administration prior to delivery—time, medication, and dose
  - I. Date and time of delivery
  - J. Number who delivered within 12, 24, 36, 48 hours from initiation of cervical ripening
  - K. Number who delivered before midnight of the following day
  - L. Meconium passage prior to delivery: yes/no, thin or thick
  - M. Total number of cervical exams
  - N. Mode of delivery
    - 1. Normal spontaneous vaginal delivery
    - 2. Vacuum assisted vaginal delivery and indication
    - 3. Forceps assisted vaginal delivery and indication
    - 4. Cesarean delivery
  - O. If a cesarean delivery was performed:
    - 1. Indication for cesarean (non-reassuring fetal heart status, umbilical cord prolapse, uterine rupture, placental abruption, failed operative delivery, arrest of dilation, arrest of descent, and other)
    - 2. Type of cesarean—emergent, urgent, or non-urgent (“Alpha,” “Beta,” or “Charlie”)

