#### **4.2 Exclusion Criteria**

1. New diagnosis requiring immediate hospitalization for monitoring (such as preeclampsia)
2. Vaginal bleeding
3. Active labor
4. Premature rupture of membranes as determined by positive ferning and as supported by pooling of fluid in the vaginal vault.
5. Uterine tachysystole (>5 contractions in 10 minutes)
6. Nonreassuring fetal heart tracing before or after Foley placement
7. Chorioamnionitis or maternal fever
8. Intrauterine fetal demise
9. Contraindication to vaginal delivery, relative or absolute (i.e. transfundal uterine surgery)
10. Abnormal placentation including a low lying placenta
11. Prior cesarean delivery
12. Intrauterine growth restriction (growth <10th percentile by formal ultrasound)
13. Known major fetal anomaly
14. Human immunodeficiency virus, Hepatitis C, or active herpes infection
15. Maternal cardiopulmonary disease requiring cardiac monitoring during labor
16. Pregestational diabetes
17. Rh isoimmunization
18. Non-English speaking

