## 4.4 Early Withdrawal of Subjects

### 4.4.1 When and How to Withdraw Subjects

A patient may be withdrawn from the study for several reasons.

First, the patient may decide at any time to cease participation in the trial. She will receive all appropriate medical cares without consequence of her participation in the trial. If she is randomized to the outpatient group, for example, but decides to withdraw before Foley placement, her induction of labor will occur in the standard, inpatient fashion. The induction will commence either that evening or the next morning, as staffing, unit flow, maternal status, and fetal status allow. Similarly, if a woman in the intervention group declines participation in the trial after the Foley catheter has been placed, the Foley catheter can be removed with pursuit of standard, inpatient cervical ripening. Alternatively, she can keep it in place and elect pain management options such as an epidural outside the realm of this study (thereby excluding her from the study and committing her to inpatient management).

Second, the patient may become excluded from the trial for several reasons. A pregnant woman may be found to be an eligible participant when she is approached at her clinic visit; however, before her scheduled induction of labor that will occur several days later, she may become excluded for any of the following reasons:

- 1) She develops a new diagnosis (such as preeclampsia) requiring immediate hospitalization for monitoring
- 2) She develops vaginal bleeding that is unexplained and concerning for labor or placental abruption
- 3) She spontaneously labors and is admitted for anticipated delivery
- 4) She undergoes premature (pre-labor) rupture of membranes
- 5) During indicated fetal heart rate monitoring, the tracing becomes non reassuring such that outpatient management is not recommended
- 6) She develops a fever and/or chorioamnionitis
- 7) There is an intrauterine fetal demise
- 8) She develops a contraindication to vaginal delivery, such as new active genital herpetic lesions
- 9) Intrauterine growth restriction is diagnosed

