Finally, the pregnant woman may become excluded from study shortly after arrival to the Family Birth Center for initiation of the planned induction of labor. Any of the above-listed reasons (vaginal bleeding, spontaneous labor, premature rupture of membranes, etc) diagnosed at presentation will be reason to exclude the woman from participation. Furthermore, *after* Foley catheter placement, a patient may be excluded from the trial should any of the following occur:

1. She is diagnosed with a condition that requires immediate admission for induction of labor (such as gestational hypertension or preeclampsia)
2. She develops vaginal bleeding more than spotting that is clinically concerning for placental abruption
3. She spontaneously labors
4. She undergoes premature rupture of membranes
5. The post-placement fetal heart tracing is non reassuring such that outpatient management is not recommended
6. She develops a fever and/or chorioamnionitis

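### The go-home instructions name no warning symptom of preeclampsia, which the protocol treats as a reason to exclude a woman and admit her: a minor safety gap that is cheap to close

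*Combined protocol and SAP*

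**What the plan says.** Section 3.1, part IV sets out the outpatient pathway for both stages of the study. IV.H states: "The fetal heart rate tracing will be monitored for 1 hour after Foley placement". IV.I then allows dismissal if the tracing is satisfactory, there is no sign of membrane rupture, labor or more than spotting, and maternal vital signs are normal. IV.K asks the woman to come back "approximately 12 hours following their Foley bulb placement". Section 6.3 item 4 repeats the vital signs on her return.

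IV.L fixes the content of the verbal and written instructions. IV.L.1 begins "To return immediately to the Family Birth Center if she feels decreased fetal movement, if she is concerned her membranes ruptured". It goes on to bleeding beyond spotting, regular painful contractions, severe pain and fever above a stated temperature, and closes with any symptom the woman finds worrying. IV.L.3 adds: "She will be provided with the 24 hour direct access line for the Family Birth Center to call with any questions or concerns".

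Hypertensive disease appears as a ground for exclusion in three places:

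- Section 4.2 item 1: "New diagnosis requiring immediate hospitalization for monitoring (such as preeclampsia".
- Section 4.4.1, list for the days before induction, item 1: "She develops a new diagnosis (such as preeclampsia) requiring immediate hospitalization for monitoring".
- Section 4.4.1, list for after catheter placement, item 1: "She is diagnosed with a condition that requires immediate admission for induction of labor (such as gestational hypertension or preeclampsia".

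The data field for unscheduled returns, section 3.3 II.C, reads: "Return to the Family Birth Center earlier than scheduled and reason (labor, rupture of membranes, decreased fetal movement, vaginal bleeding, pain, fever, or other".

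**The concern.** The study sends women home during a phase that the comparison group spends in hospital. While they are at home, recognising a problem depends largely on the woman herself, and the instruction list is the main tool she is given. The protocol regards new preeclampsia as incompatible with continuing in the study, and in the post-placement list it ties gestational hypertension and preeclampsia to immediate admission. Yet the list tells her nothing about how preeclampsia might announce itself.

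A catch-all works only if she already knows that a symptom matters. A headache is easy to dismiss, and IV.J.2 lets her take Tylenol for pain as needed while the catheter is in place. What is at stake is delayed recognition of a condition that the protocol would want managed in hospital. This concerns participant safety, not inference.

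**Working it through.** The plan gives no figure on this point. The check is a comparison of texts and one subtraction.

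**Step 1: the interval without a scheduled check.** Inputs: return at about 12 h after placement (3.1 IV.K) and 1 h of monitoring after placement (3.1 IV.H).

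Time at home = 12 h − 1 h = about 11 h.

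This takes the dismissal vital signs as measured at the end of the monitored hour; IV.I requires them to be normal but does not fix the minute. Travel time and early return shorten the time at home. For a woman who arrives at the 1930 slot (IV.A), most of the interval is overnight.

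**Step 2: what the instructions name.** IV.L.1 contains six named triggers and one general one: (1) decreased fetal movement, (2) suspected membrane rupture, (3) bleeding beyond spotting, (4) regular painful contractions, (5) severe pain, (6) fever, and (7) anything worrying. None of the six refers to headache, visual change, upper abdominal pain or blood pressure. Severe pain would take in severe upper abdominal pain without saying so.

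**Step 3: whether another step covers it.** The standard questions on arrival (3.1 IV.E) cover contractions, fetal movement, bleeding, fluid leakage, and fever or chills, but no hypertensive symptom. Vital signs are taken on arrival (6.2 item 6), must be normal for dismissal (IV.I) and are repeated on return (6.3 item 4). Raised blood pressure present before dismissal should therefore be caught. What remains is disease that develops, or first causes symptoms, after she leaves.

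**Step 4: whether such a return would be recorded.** Section 3.3 II.C has six named reasons and an open category. A return for these symptoms would go under the open category, and section 8.2 requires all adverse events to be recorded. No information is lost.

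**Step 5: a bound on the cost of the remedy.** Section 7.2 plans 40 outpatient women and a 4 h difference (16 to 12 h). Suppose one extra woman returns at the very start of the interval, is kept in, and delivers when she would have anyway. She adds at most about 11 h to her own total. The outpatient mean moves by 11 / 40 = 0.275 h, which is 0.275 / 4 = about 7% of the planned difference. A later return, or an earlier delivery because of it, adds less.

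**The case against.** The strongest reply is that the list follows the risks of the device. Section 1.4 gives those risks as discomfort, spotting, membrane rupture, spontaneous labor and abruption, and says a woman who has one of the last three at home comes straight back as instructed. IV.L.1 covers these and adds fever and fetal movement. Nothing in the documents calls preeclampsia a consequence of the catheter, so leaving it unnamed may be deliberate. That explains the list, but it does not remove the reason to extend it: the post-placement list in 4.4.1 names hypertensive disease, and the hours at home exist because of the study.

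A reader might also set the six post-placement exclusions in 4.4.1 against the return triggers, count five matches and one miss, and conclude that the protocol contradicts itself. The documents do not support that. The 4.4.1 list gives clinicians' grounds for exclusion and follows a sentence about women excluded soon after arrival. Nothing says the home instructions should mirror it. The count of five also depends on letting decreased fetal movement stand in for a non-reassuring tracing, although no tracing is taken at home.

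Three further points stand. A route back already exists through the catch-all, the severe-pain item and the 24-hour line. The handout itself is not among the documents, so only the content prescribed by IV.L can be judged. What women are told about preeclampsia in routine antenatal care is likewise unseen.

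**Conclusion.** The point holds as a minor safety improvement. The protocol treats new preeclampsia, and after placement gestational hypertension too, as a reason to exclude and admit, but the return instructions name no symptom of it for the roughly 11 h between the dismissal check and the check on return.

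The documents give no rate of preeclampsia arising at home, so the number of women affected cannot be estimated. All 40 planned outpatient women would receive these instructions. The conclusion rests on two assumptions: that the written sheet follows IV.L as the protocol says, and that the symptoms proposed below are suitable warnings. The second is general clinical knowledge, not something the documents state.

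A reader might infer that affected women have no way back, or that the omission biases the comparison. Neither follows. The catch-all and the telephone line are explicit, and the gap has no shown effect on power, comparability or the primary result. The missing category in 3.3 II.C is not a fault either, because the open category captures the event.

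**What to change.** In section 3.1 IV.L.1 and the written instructions, add severe headache, visual disturbance or upper abdominal pain to the reasons for immediate return. If the unit already has a preeclampsia warning list, use that instead so that the wording matches local practice.

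The cost is one line of text. It adds no visit or test and excludes nobody. A few more women may return early, and their hours would count toward the primary endpoint, within the bound of about 0.275 h on the outpatient mean per extra return. The change has a limit: it cannot detect raised blood pressure that causes no symptoms, so it only partly covers gestational hypertension.

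Optionally, add a preeclampsia-symptom code to 3.3 II.C to keep the data field in step with the list. The change to the instructions is worth making without it.
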